1.0 OBJECTIVES

This study will enroll two separate cohorts to assess the efficacy of pembrolizumab (MK-3475) in desmoplastic melanoma (DM). **Cohort A** will evaluate pembrolizumab (MK-3475) as neoadjuvant therapy for patients with DM that is deemed resectable by the treating investigator; including primary DM, locally advanced DM, and locally recurrent DM. **Cohort B** will be a pilot study to evaluate the use of pembrolizumab (MK-3475) for patients with DM that is deemed unresectable by the treating investigator, including metastatic DM.

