5.2 Prior/Concurrent Therapy Criteria

- a. Patients must not have received prior systemic treatment for this melanoma.
- b. Patients must not be planning to receive concomitant other biologic therapy, hormonal therapy, other chemotherapy, anti-cancer surgery or other anti-cancer therapy while on this protocol.
- c. Patients must not have received radiation therapy, non-cytotoxic agents or investigational agents or systemic corticosteroids within 14 days prior to registration.
- d. Patients may have received prior surgery. All adverse events associated with prior surgery must have resolved to ≤ Grade 1 (per CTCAE 4.0) prior to registration

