The study will examine adaptive immune resistance by first evaluating whether PD-L1 expression is increased at Week 4 and resection as compared to baseline using paired t-tests and controlling the type I error at the two-sided alpha=0.05 level. With 25 patients, we anticipate 80% power at each time point to detect a mean difference in expression of 0.58 standard deviations. We will further evaluate whether increased PD-L1 expression at Week 4 or at resection is associated with response. Specifically, we will compute the change in expression from baseline to resection and then compare the change between responders and non-responders using a two-sample t-test. We will control type I error at the two-sided alpha=0.05 level. Assuming that 25% of patients respond then at each time point we anticipate 80% power to detect a difference in mean PD-L1 expression change of 1.35 standard deviations. We will repeat the analysis comparing the change in PD-L1 expression from baseline to week 4 to determine whether T-cell infiltration in the on-treatment biopsy is associated with response at resection. In addition to our assessment of overall mutational load, we will further conduct a neoantigen analysis. Specifically, we will predict the immunogenicity of each nonsynonymous somatic mutation using NetMHC. We will then use logistic regression to regress pCR status on the number of predicted immunogenic mutations, computing a pvalue using a 1-df test and controlling type I error at the two-sided alpha=0.05 level.

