To assess the hypothesis that ctDNA fraction at baseline and week 4 are associated with response in DM patients, we will assess the association between response and ctDNA fraction using a two-sample t-test at the two-sided $\alpha = 0.05$ level. Assuming that 20% of patients respond, then we anticipate 80% power to detect a difference in mean ctDNA fraction of 1.61 standard deviations.

To assess the hypothesis that TCR clonality is higher in DM patients who respond, suggesting that the T-cells are targeting the tumor, we will compute the clonality metric as the normalized Shannon entropy for all patients at baseline, Week 4, and progression. We will then compute the change in clonality metric from baseline to progression. The change in clonality will be compared between responders and non-responders using a two-sample t-test with significance determined at the two-sided alpha=0.05 level. Assuming that 20% of patients respond, then we anticipate 80% power to detect a difference in clonality change of 1.61 standard deviations. We will repeat the analysis comparing the change in clonality from baseline to Week 4 to determine whether T-cell clonality in the on-treatment biopsy is associated with response at progression.

The study will examine adaptive immune resistance by first evaluating whether PD-L1 expression is increased at Week 4 and progression as compared to baseline using paired t-tests and controlling the type I error at the two-sided alpha=0.05 level. With 21 patients, we anticipate 80% power at each time point to detect a mean difference in expression of 0.64 standard deviations. We will further evaluate whether increased PD-L1 expression at Week 4 or at progression is

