15.0 SPECIAL INSTRUCTIONS

15.1 Specimen Submission for Translational Medicine

Specimens for Translational Medicine studies outlined in Section 18.1 are required for participation in this study.

- a. Specimens must be submitted at the timepoints listed below. Collection instructions are outlined in Section 15.1c and submission instructions are outlined in Section 15.1e. NOTE: With patient consent, leftover specimens will be banked for future unknown use.
- b. Specimens must be submitted at the following times (see Section 9.0):
 - 1. Three cores (at least 18 gauge needle) to be obtained from primary (preferred) or metastatic lesions (avoid lymph node biopsy if possible) and made into three different FFPE blocks (one core per block). Sending all three blocks is preferred. Thirty slides (minimum bum thick) per block from each of the blocks may be submitted if the institution cannot release pathology paraffin embedded blocks, at the following times:
 - Baseline (required) prior to the start of study treatment. Initial/Archival biopsy may be used if 4 cm x 30 slides can be provided). Submit tissue within 30 days after registration.
 - Biopsy between 3 and 5 weeks after initiation of treatment (required for all patients with residual disease to biopsy). Submit tissue within 30 days of collection.
 - Surgical specimen from each site of surgical resection (required if surgical resection is performed). Submit tissue within 30 days of collection.
 - Progression/relapse (optional). Submit tissue within 30 days of collection.

[figure not shown]
Submit formalin fixed paraffin embedded (FFPE) tissue according to guidelines below.

- 2. Twenty mL whole blood in vacutainer tubes with EDTA coating. Collect at the following times:
 - Baseline (mandatory prior to the start of study treatment)

Specimen Collection Instructions

- Standard collection of Paraffin Embedded Tissue Block.
 - Place the fresh tissue in formalin. Do Not Exceed 24 hours fixation time.
 - Fixed tissue must be paraffin embedded within 24 hours.
 - Send H & E (Hematoxylin and Eosin) stained section if it is routine practice for the site. Otherwise, sending the block without the H&E slide is adequate.

- 2. Standard collection of Slides.
 - Slides may be processed according to local pathology guidelines.
- 3. Standard Instructions for Shipping Paraffin Embedded Tissues and Slides:
 - Include in shipment:
 - i. Tissue as outlined above

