For packaging instructions, refer to the shipping guidelines for ambient specimens in the General Specimen Submission Instructions outlined below.

- d. Specimen collection kits are not being provided for this submission; sites will use institutional supplies.
- e. SHIPPING SAMPLES
 - 1. All submitted specimens must be labeled with the treatment protocol number, SWOG patient number, patient initials, time point, and date of specimen collection, specimen number and/or specimen type, Surgical Pathology ID (Accession # from pathology report), and block number (as applicable).
 - a. Instructions for Labels
 - Large Labels:
 - Use Avery 5160 labels*
 - Use for all specimens submitted
 - Type or write information
 - Place on outside bag or container, depending on specimen type
 - ii. Small Labels:
 - Use Avery 5160 labels*
 - Use for all specimens submitted
 - Type or write information on right side of line
 - Cut the label on the line
 - Place only the right side of the label on each specimen
 - For blood products, place on each vial submitted
 - For paraffin specimens, place on slides or blocks

*If Avery 5160 labels are not available, the label may be printed on regular paper and taped to the specimen container.

2. Include a specimen shipping form in every shipment, ensuring the information on the form exactly matches the specimens in the shipment.

- 3. Ship specimens according to IATA shipping regulations.
 - a. Shipping guidelines for ambient specimens:
 - The specimen must be wrapped in absorbable material.
 - ii. Place the specimen in an AIRTIGHT container (must have a primary and secondary container, ex a Saf-T-Pak).
 - iii. Place packaged specimen in an appropriate shipping container (ex. FedEx box or clinical pack).

Mark the outside shipping container with an "Exempt Human Specimen" label.

4. SWOG Specimen Tracking System (STS)

All specimen submissions for this study must be entered and tracked using the SWOG online Specimen Tracking system. SWOG members may log on the online system via the CRA Workbench. To access the CRA Workbench, go to the SWOG Web site (http://swog.org) and logon to the Members Area. After you have logged on using your SWOG roster ID number and password, click on the *CRA Workbench* link to access the home page for CRA Workbench website. Non-SWOG users may log into SpecTrack using their CTSU UserID and password on the SpecTrack login page located at

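### Baseline and later tissue samples need not come from the same lesion or period, so a tissue-source difference can enter the paired PD-L1 change, and Section 11 makes no allowance for it

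*Combined protocol and SAP*

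**What the plan says.** **Tissue source (Section 15.1b).** Cores are "to be obtained from primary (preferred) or metastatic lesions (avoid lymph node biopsy if possible"). One rule covers all collection times. For baseline, "Initial/Archival biopsy may be used if 4 cm x 30 slides can be provided"; the only condition is the amount of tissue. The on-treatment sample is described as "Biopsy between 3 and 5 weeks after initiation of treatment (required for all patients with residual disease to biopsy"), with no lesion specified.

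**Labels (Section 15.1e).** Required fields include "time point, and date of specimen collection, specimen number and/or specimen type, Surgical Pathology ID". Lesion or anatomic site is not among them. Section 15.2b does require slides sent for central confirmatory review to be marked primary, metastatic or normal.

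**Who is enrolled.** Section 1.0 describes Cohort A as "including primary DM, locally advanced DM, and locally recurrent DM" and says Cohort B includes metastatic disease. Section 5.2 adds: "Patients may have received prior surgery". Prior systemic treatment for this melanoma is excluded.

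**Analysis.** Section 11.1d begins the adaptive-resistance analysis by "evaluating whether PD-L1 expression is increased at Week 4 and resection as compared to baseline using paired t-tests", and Section 11.2d has the matching Cohort B analysis at week 4 and progression. For Cohort B, "With 21 patients, we anticipate 80% power at each time point to detect a mean difference in expression of 0.64 standard deviations"; for Cohort A the figure is 0.58 SD with 25 patients. Changes in CD8, TCR clonality and PD-L1 are also compared between responders and non-responders by two-sample t-test.

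Sections 9.1, 9.2, 11, 15.1 and 18.1 contain no same-lesion rule and no age limit for archival tissue. Section 11 has no covariate, restriction or sensitivity analysis for tissue source.

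**The concern.** Appendix 18.1 asks whether PD-1 blockade induces PD-L1 and whether it raises CD8+ infiltration. With no control arm, each patient's own baseline is the only comparator for those questions. It works as a comparator only if baseline and later samples differ mainly by treatment.

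The protocol lets them differ in other ways. A Cohort B patient could contribute an archival primary as baseline and a metastasis at week 4. A Cohort A patient with a local recurrence could contribute tissue from the earlier excision. The measured change is then the drug effect plus any difference due to lesion or tissue age. If that difference has a direction on average, the paired PD-L1 test can suggest induction where there is none, or hide it. If it has no direction, it widens the spread of the changes and costs power.

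**Working it through.** **Inputs.** From 11.1d and 11.2d: two-sided alpha 0.05; paired test n=25 at 0.58 SD (Cohort A) and n=21 at 0.64 SD (Cohort B); two-sample effects of 1.35 SD with 25% of 25 responding and 1.61 SD with 20% of 21 responding. The documents give no between-lesion SD, no archival shift and no mismatch frequency, so those are assumed and shown as ranges.

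**Formulas.** Exact noncentral t.
- Paired: df = n − 1, noncentrality = d√n.
- Two-sample: df = n1 + n2 − 2, noncentrality = d/√(1/n1 + 1/n2).

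**Step 1: the plan's own figures.**
- Paired, n=25: noncentrality 0.58 × 5 = 2.90, power 79.5%.
- Paired, n=21: 0.64 × √21 = 2.93, power 79.7%.
- Two-sample, Cohort A, 1.35 SD: 79.9% with 6.25 v 18.75, and 78.8% with 6 v 19.
- Two-sample, Cohort B, 1.61 SD: 79.9% with 4.2 v 16.8, and 78.5% with 4 v 17.

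The stated figures reproduce.

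**Step 2: systematic shift, no drug effect, paired PD-L1 test.** Put the average shift b, in SDs of the change, in place of d. The rejection rate should be 5%.

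| Average shift b | n=25 | n=21 |
|---|---|---|
| 0.1 SD | 7.7% | 7.2% |
| 0.2 SD | 16.1% | 14.1% |
| 0.3 SD | 30.2% | 25.8% |

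The average depends on how many pairs are affected. If a fraction f of pairs is mismatched and those pairs shift by 0.5 SD, the mean is 0.5f and the SD is √(1 + f(1 − f) × 0.25). At n=25:
- f = 25%: 0.125/1.023 = 0.122 SD, rejection 9.0%.
- f = 50%: 0.25/1.031 = 0.243 SD, rejection 21.4%.

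**Step 3: noise only.** Suppose the stated SD refers to matched samples and mismatch adds a fraction v to the overall variance of change. The standardised effect becomes d/√(1 + v).

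| Added variance v | Paired, n=25, 0.58 SD | Paired, n=21, 0.64 SD | Two-sample, 6 v 19, 1.35 SD |
|---|---|---|---|
| 10% | 75.6% | 75.8% | 74.9% |
| 25% | 70.2% | 70.4% | 69.5% |
| 50% | 62.3% | 62.5% | 61.6% |
| 100% | 50.3% | 50.6% | 49.7% |

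**Step 4: would restricting to same-lesion pairs be better?** Take n=25, 0.58 SD, and assume each mismatched pair has twice the variance.
- Half mismatched: overall variance 1 + 0.5 = 1.5, so all pairs give about 62%. The 13 matched pairs alone give 48.5%.
- A quarter mismatched: overall variance 1.25, so all pairs give about 70%. The 19 matched pairs alone give 66.7%.

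On noise alone, restriction loses power. Its value is in removing a systematic shift.

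**The case against.** Several points on the other side stand.

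- **Not every change analysis is biased.** A reader might infer that it is. A lesion or age shift unrelated to response cancels between responders and non-responders and leaves only noise. Bias there needs lesion choice or archival use to depend on response. A route exists: the week 3-5 sample needs residual disease, so if the baseline lesion regresses, a later sample must come from one that persists. The documents do not show that this happens.
- **The drug effect does not disappear.** It is tempting to say that a mismatched pair measures lesion and time instead of PD-1 blockade. It measures both together.
- **The 80% power statements are not wrong.** They are in SD units with no source named for the SD, so they hold for whatever SD of change applies. The losses in Step 3 arise only if that SD was meant for matched tissue. The 50% figure is the case where the overall variance doubles.
- **The protocol already limits the problem.** The primary is preferred at every collection time, prior systemic treatment is excluded, and Cohort A is resectable local disease in which a second lesion is less likely. An archival baseline remains possible in both cohorts.
- **Some of the needed information is already collected.** Collection date and pathology identifier are on the label and a pathology report accompanies the tissue. Lesion site is not a required label field.

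**Conclusion.** The gap is real and modest. The text permits mismatched pairs, and nothing in the analysis plan would detect or allow for them. The paired PD-L1 test is the most exposed: under assumed average shifts of 0.1 to 0.3 SD its false-positive rate runs from 7.7% to 30.2% at n=25 and from 7.2% to 25.8% at n=21. For the responder comparisons the expected harm is lost precision, with bias only under the dependence described above.

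The sizes rest on assumed shifts and variances, and the frequency of mismatch cannot be read from the documents. It is more likely in Cohort B. Only the Other objectives in Section 1.3 are affected; the pCR and CR designs are not. The documents do not support a claim that the results would be uninterpretable, or that same-lesion pairs should become the main analysis set.

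**What to change.** 1. **Section 15.1b:** ask that the week 3-5 cores come from the lesion sampled at baseline where it remains.
2. **Section 15.1e:** add lesion site to the specimen label. Archival status can be derived from the collection date already required.
3. **Sections 11.1d and 11.2d:** keep all available pairs as the main change analysis. Pre-specify a sensitivity analysis limited to same-lesion pairs with non-archival baseline tissue, and report the number of such pairs in each cohort.

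No extra biopsy is needed. The cost is one label item and a small additional analysis. The restricted set will be imprecise, so it should be read for the direction and size of the change, not for significance.

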16.0 ETHICAL AND REGULATORY CONSIDERATIONS

The following must be observed to comply with Food and Drug Administration regulations for the conduct and monitoring of clinical investigations; they also represent sound research practice:

Informed Consent

The principles of informed consent are described by Federal Regulatory Guidelines (Federal Register Vol. 46, No. 17, January 27, 1981, part 50) and the Office for Protection from Research Risks Reports: Protection of Human Patients (Code of Federal Regulations 45 CFR 46). They must be followed to comply with FDA regulations for the conduct and monitoring of clinical investigations.

Institutional Review

This study must be approved by an appropriate institutional review committee as defined by Federal Regulatory Guidelines (Ref. Federal Register Vol. 46, No. 17, January 27, 1981, part 56) and the Office for Protection from Research Risks Reports: Protection of Human Patients (Code of Federal Regulations 45 CFR 46).

Drug Accountability

An investigator is required to maintain adequate records of the disposition of investigational drugs according to procedures and requirements governing the use of investigational new drugs as described in the Code of Federal Regulations 21 CFR 312.

Publication and Industry Contact

The agent(s) supplied by CTEP, DCTD, NCI used in this protocol is/are provided to the NCI under a Collaborative Agreement (CRADA, CTA, CSA) between Merck (hereinafter referred to as "Collaborator(s)") and the NCI Division of Cancer Treatment and Diagnosis. Therefore, the following obligations/guidelines in addition to the provisions in the "Intellectual Property Option to Collaborator"

(http://ctep.cancer.gov/industryCollaborations2/intellectual property.htm) contained within the terms of award apply to the use of the Agent in this study:

- 1. Agent(s) may not be used for any purpose outside the scope of this protocol, nor can Agent(s) be transferred or licensed to any party not participating in the clinical study. Collaborator(s) data for Agent(s) are confidential and proprietary to Collaborator(s) and shall be maintained as such by the investigators. The protocol documents for studies utilizing Agents contain confidential information and should not be shared or distributed without the permission of the NCI. If a copy of this protocol is requested by a patient or patient's family member participating on the study, the individual should sign a confidentiality agreement. A suitable model agreement can be downloaded from: http://ctep.cancer.gov.
- 2. For a clinical protocol where there is an investigational Agent used in combination with (an)other investigational Agent(s), each the patient of different Collaborative Agreements, the access to and use of data by each Collaborator shall be as follows (data pertaining to such combination use shall hereinafter be referred to as "Multi-Party Data"):
 - a. NCI will provide all Collaborators with prior written notice regarding the existence and nature of any agreements governing their collaboration with NCI, the design of the proposed combination protocol, and the existence of any obligations which would tend to restrict NCI's participation in the proposed combination protocol.
 - b. Each Collaborator shall agree to permit use of the Multi-Party Data from the clinical trial by any other Collaborator solely to the extent necessary to allow said other Collaborator to develop, obtain regulatory approval or commercialize its own Agent.
 - c. Any Collaborator having the right to use the Multi-Party Data from these trials must agree in writing prior to the commencement of the trials that it will use the Multi-Party Data solely for development, regulatory approval, and commercialization of its own Agent.
- 3. Clinical Trial Data and Results and Raw Data developed under a Collaborative Agreement will be made available exclusively to Collaborator(s), the NCI, and the FDA, as appropriate and unless additional disclosure is required by law or court order as described in the IP Option to Collaborator (http://ctep.cancer.gov/industryCollaborations2/intellectual_property.htm). Additionally, all Clinical Data and Results and Raw Data will be collected, used and disclosed consistent with all applicable federal statutes and regulations for the protection of human patients, including. If applicable, the Standards for Privacy of Individually Identifiable Health Information set forth in 45 C.F.R. Part 164.
- 4. When a Collaborator wishes to initiate a data request, the request should first be sent to the NCI, who will then notify the appropriate investigators (Group Chair for Cooperative Group studies, or PI for other studies) of Collaborator's wish to contact them.
- 5. Any data provided to the Collaborator(s) for Phase III studies must be in accordance with the guidelines and policies of the responsible Data Monitoring Committee (DMC), if there is a DMC for this clinical trial.
- 6. Any manuscripts reporting the results of this clinical trial must be provided to CTEP by the Group office for Cooperative Group studies or by the principal investigator for non-Cooperative Group studies for immediate delivery to Collaborator(s) for advisory review and comment prior to submission for publication. Collaborator(s) will have 30 days from the date of receipt for review. Collaborator shall have the right to request that publication

be delayed for up to an additional 30 days in order to ensure that Collaborator's confidential and proprietary data, in addition to the Collaborator(s)'s intellectual property rights, are protected. Copies of abstracts must be provided to CTEP for forwarding to Collaborator(s) for courtesy review as soon as possible and preferably at least three (3) days prior to submission, but in any case, prior to presentation at the meeting or publication in the proceedings. Press releases and other media presentations must also be forwarded to CTEP prior to release. Copies of any manuscript, abstract and/or press release/media presentation should be sent to:

E-mail: [contact]

The Regulatory Affairs Branch will then distribute them to the Collaborator(s). No publication, manuscript or other form of public disclosure shall contain any of the Collaborator's confidential/proprietary information.

Monitoring

This study will be monitored by the Clinical Data Update System (CDUS) Version 3.0. Cumulative CDUS data will be submitted quarterly to CTEP by electronic means. Reports are due January 31, April 30, July 31 and October 31.

Confidentiality

Please note that the information contained in this protocol is considered confidential and should not be used or shared beyond the purposes of completing protocol requirements until or unless additional permission is obtained.

